6.2 Secondary Endpoints

- 1. Percent reduction in inflammatory lesion count at week 16 compared to baseline.
- 2. Percent reduction in non-inflammatory lesion count at week 16 compared to baseline.
- 3. Percent reduction in total lesion count at week 16 compared to baseline.

6.2.2 Tolerability

The Investigator will grade the current severity of erythema (disease related and/or related to retinoid use), dryness, peeling, and oiliness as per the following:

Score	Erythema	Dryness	Peeling	Oiliness
0 = Absent	No redness	None	Smooth	Normal
1 = Trace	Faint red or pink coloration, barely perceptible	Barely perceptible dryness by palpation with no accentuation of skin markings, skin desquamation (flakes) or fissure formation	Fine peeling, barely perceptible	Mild and localized
2 = Mild	Light red or pink coloration	Easily perceptible dryness by palpation with accentuation of skin markings but no skin desquamation (flakes) or fissure formation	Slight peeling	Mild and diffuse
3 = Moderate	Medium red coloration	Easily noted dryness with accentuation of skin markings and skin desquamation (small flakes) but no fissure formation	Definitely noticeable peeling	Moderate and diffuse
4 = Severe	Beet red coloration	Easily noted dryness with accentuation of skin markings, skin desquamation (large flakes) and/or fissure formation	Extensive peeling	Prominent and dense

The **Investigator** will **interview the subject** to determine the current severity of pruritus and burning; these symptoms will be graded as per the following:

Score	Description	
0 = Absent	Normal, no discomfort	
1 = Trace	An awareness, but no discomfort and no intervention re	quired
2 = M ild	Noticeable discomfort causing intermittent awareness	
3 = Moderate	Noticeable discomfort causing continuous awareness	
4 = Marked	Definite discomfort causing continuous awareness inter-	fering occasionally with normal daily activities
5 = Severe	Definite, continuous discomfort interfering with normal d	aily activities

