1 GENERAL INFORMATION

1.1 Introduction

Truncal acne is an under diagnosed and under treated condition. Aczone gel 7.5% has already been approved for the treatment of acne vulgaris. However, topical treatment of truncal acne is very difficult in traditional vehicles due to the difficulty of covering large body surface areas. The recent approval of Aczone gel 7.5% foam gives us an opportunity to address this unmet need. Therefore, the current pilot study will investigate the efficacy and safety of Aczone 7.5% gel in the treatment of truncal acne.

Truncal acne is estimated to occur in 61 percent and 45 percent of acne patients, respectively. 1.2 The pathophysiology of truncal acne is the same as facial acne, and both respond similarly to therapy. However, despite a wide range of treatment options available, the management of truncal acne remains challenging. Clinicians tend to emphasize oral therapies over topical interventions for truncal acne as it is typically assumed oral medications are more convenient than applying topical applications to large and potentially hard-to reach body areas. This line of reason is based on using standard creams or gels and does not necessarily hold-up with the advent of foam formulations that are significantly more convenient in treating hard-to-reach areas and larger surface areas. In fact, foam vehicles are associated with improved usability, better adherence and, consequently, improved therapeutic results. 5,6,7,8,9,10,11,12 Aczone gel 7.5% has been approved by the FDA for the treatment of acne vulgaris in individuals who are older than 12 years of age. Aczone gel 7.5% have been used on the chest and back acne during the phase III clinical trials but its efficacy has not been an endpoint in this study. It is reasonable to assume that Aczone gel 7.5% could present to be a viable treatment option for truncal acne. The current pilot study will investigate the efficacy and safety of Aczone gel 7.5% in the treatment of truncal acne. Based on the recent phase III clinical study of aczone gel 7.5%, it is expected that the typical risk/benefit profile of aczone gel 7.5% should apply in the treatment of truncal acne (ie, reduction in acne signs and symptoms, with possible adverse effects such as burning, stinging, tingling, pruritus, dry skin, erythema and/or edema).

- 1. Thomas DR. Psychosocial effects of acne. J Cutan Med Surg. 2004;8 Suppl 4:3-5.

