2 STUDY OBJECTIVES

The objectives of this study are to observe the efficacy and safety of Aczone gel 7.5% as a treatment modality for moderate truncal acne.

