3 STUDY DESIGN

This is a three-center, open-label pilot study ([name] Louisville, KY, [name], DO, Las Vegas, NV & [name] Sacramento, CA.). All study subjects will receive Aczone gel 7.5% at Visit 1. The duration of the study is 16 weeks and consists of a Screening, Baseline Visit, and three (3) Follow-up Visits at Weeks 4, 10, and 16.

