5.2 Study Treatment

5.2.1 Details of Study Treatment

ACZONE (dapsone) Gel, 7.5%, contains dapsone, a sulfone, in an aqueous gel base for topical dermatologic use. ACZONE Gel, 7.5% is an off-white to yellow gel with suspended particles. Chemically, dapsone has an empirical formula of C₁₂H₁₂N₂O₂S. It is a white or slightly yellow-white, crystalline powder that has a molecular weight of 248.30. Each gram of ACZONE Gel, 7.5%, contains 75 mg of dapsone, USP, in a gel of diethylene glycol monoethyl ether, methylparaben, acrylamide/sodium acryloyldimethyl taurate copolymer, isohexadecane, polysorbate 80, and purified water.

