10 SUPPLEMENTS

I Prohibited Medications / Wash-Out Periods

SUPPLEMENT I Prohibited Medications / Wash-Out Periods

Use of the following medications (concurrent and contraindicated treatments) are prohibited during the course of the study and appropriate wash-out periods must be respected:

100 C	Medication	Washout
Topical	Retinoids, antibiotics, BPO, dapsone, bleaching agents	2Weeks washout prior to V1
ОТ	C acne medications or bleaching agents	1Week washout prior to V1

Oral Antibiotics for acne	4Weeks washout prior to V1
Oral Retinoids	24Weeks washout prior to V1
Cryotherapy, chemical peels, microdermabrasion	2Weeks washout prior to V1
Laser Resurfacing and dermabrasion	24Weeks washout prior to V1
Investigational Drugs	4Weeks washout prior to V1

ACZ1601 (01JUN2016) Page 13 of 14

SUPPLEMENT II

Patient's Preference Questionnaire

The aim of this questionnaire is to find out what you like and what you don't like about different types of skin medications that you have used.

1. For all skin medicines you have used in the past, please rate the following treatments in the order you preferred them:

(1= "liked the best", 2= "second best", 3= "third best", 4= "fourth best, 5= "liked the least". If you have not used a certain type of skin medicine, please enter N/A for does not apply to me.)

Gel Lotion Cream Ointment Spr	ray
-------------------------------	-----

2. Please rate the following qualities of the gel, compared to the other skin medicines you have used in the past

(If you have not had a previous experience with other skin medicines, please circle N/A for does not apply to me.)

	Very Inferior "Much Worse"	Inferior "Worse"	About the same	Better	Superior "Much Better"	Does Not Apply to Me
Gel is easy to use	1	2	3	4	5	N/A
I am able to continue daily activities right away following putting the medicine on my skin (i.e., getting dressed, doing school work, playing etc.)	1	2	3	4	5	N/A
The gel leaves my skin feeling soft	1	2	3	4	5	N/A
I am able to apply the gel to large body surface areas	1	2	3	4	5	N/A
The gel disappears into my skin quickly when I apply it	1	2	3	4	5	N/A

3. Please rate the gel on each of the following:

	Very Poor	Poor	Fair	Good	Excellent	Does Not Apply to Me
Moisturizing ("It leaves my skin feeling soft and smooth")	1	2	3	4	5	N/A
Lack of residue ("There is nothing left on my skin")	1	2	3	4	5	N/A
Does not feel greasy	1	2	3	4	5	N/A
Absorbs quickly ("Disappears into my skin quickly after I put it on my skin")	1	2	3	4	5	N/A

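### The erythema item in Section 6.2.2 is tied to acne or retinoid use, in a trial that bans retinoids and treats everyone with dapsone gel; read literally, it leaves out redness caused by the gel

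*Combined protocol and SAP*

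**What the plan says.** Section 6.2.2 (Tolerability) asks the investigator to grade the current "severity of erythema (disease related and/or related to retinoid use), dryness, peeling, and oiliness as per the following". A 0-4 table follows, in which each erythema grade is described by colour alone.

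Other parts of the document bear on the two causes in that parenthesis:

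- **Retinoids.** Supplement I says that the listed medications "are prohibited during the course of the study and appropriate wash-out periods must be respected". The topical row reads "Retinoids, antibiotics, BPO, dapsone, bleaching agents", with a 2-week wash-out before Visit 1. A separate row, "Oral Retinoids", carries a 24-week wash-out.
- **Study treatment.** Section 3: "All study subjects will receive Aczone gel 7.5% at Visit 1". Section 5.2.1: "ACZONE (dapsone) Gel, 7.5%, contains dapsone, a sulfone, in an aqueous gel base for topical dermatologic use". No retinoid is among the ingredients listed there.
- **Expected effects of the gel.** Section 1.1 describes its risk/benefit profile "with possible adverse effects such as burning, stinging, tingling, pruritus, dry skin, erythema and/or edema".
- **Objective.** Section 2 sets out "to observe the efficacy and safety of Aczone gel 7.5% as a treatment modality for moderate truncal acne".

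The tolerability footnote to the visit schedule (Section 5.1.1; its text is printed after the Visit 1 list in 5.1.2) names six items: peeling, erythema, dryness, oiliness, burning and pruritus. It attaches no cause to any of them.

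**The concern.** A tolerability item should pick up local reactions to the product under test. Here the parenthesis names one drug class, which subjects may not use, and omits the one product that all of them use. Gel-induced redness is neither disease related nor retinoid related, and no other section extends the parenthesis to it.

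At stake is how the erythema score can be read. Section 8.2 calls for descriptive summaries of the variables collected, so the score will be reported, and safety is part of the stated objective. If some investigators at the three centers grade by colour and others first exclude redness that they attribute to the gel, the summary mixes two different measurements. With a single arm there is no control group in which under-grading would show.

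**Working it through.** The plan gives no figure to reproduce, and the point depends on none. The check is a comparison of the sections.

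**Step 1: does the named drug belong in the trial?** No. Retinoids are prohibited throughout (Supplement I), and the study gel lists none (Section 5.2.1). One narrow use for the phrase remains. Topical retinoids need be stopped only 2 weeks before Visit 1, and the documents do not say how long retinoid redness lasts, so residual redness at baseline is not excluded. That does not explain why the study gel is left out.

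**Step 2: is redness from the gel foreseen?** Yes, in Section 1.1.

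**Step 3: what does each text do with each source of redness?**

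| Source of redness | Parenthesis read literally | Colour anchors (6.2.2) | Adverse event route (7.1, 7.2.2) |
|---|---|---|---|
| Acne | graded | graded | recorded if new or worse |
| Retinoid (prohibited) | graded | graded | recorded if new or worse |
| Study gel | outside the item | graded | recorded if new or worse |
| Any other cause | outside the item | graded | recorded if new or worse |

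The two readings part in the last two rows. For redness due to the gel alone, the literal reading leads to grade 0 and the anchors to whichever of grades 1 to 4 the colour matches. The gap is then the full observed grade, which is a worst case and not an expected difference. The last row can arise at baseline too, so a correction has to cover that visit.

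**Step 4: what else captures gel redness?** Section 7.1 defines adverse events without regard to cause, provided that the condition is new or worse than before the study. Section 7.2.2 has the investigator record severity, and Section 8.2 has incidence and severity tabulated. No erythema scale is attached to that severity; the only anchored one is in 6.2.2.

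**Step 5: what depends on the score?** Neither the primary endpoint (6.1, based on the truncal IGA) nor the three listed secondary endpoints (6.2, lesion counts) uses it. No erythema grade appears among the discontinuation circumstances in Section 4.3.

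**The case against.** The strongest reply is that raters will simply grade what they see. The item sits under Tolerability and asks for current severity. Grade 0 is anchored to the absence of redness, so scoring visibly red skin as 0 contradicts the anchor. The footnote is unqualified, the parenthesis does not say that other causes are excluded, and the protocol gives no procedure for dividing redness by cause. In subjects with moderate acne, the disease-related part already covers much of the redness seen. This stands: it makes the literal reading less likely. It does not remove the conflict, because the protocol does not say whether the parenthesis or the anchors govern.

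A reader might also infer that the trial would lose its safety signal for gel-induced erythema. The documents do not support that. The gel is first dispensed at Visit 1, after a 2-week wash-out of topical dapsone, so redness it causes will normally be new or worse and will be recorded as an adverse event. The exception is gel redness that takes the place of resolving acne redness with no net worsening. What could be lost is a grade on the anchored scale.

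A reader might try to size the problem by counting assessments: 30 subjects x 4 visits = 120 erythema gradings if nobody drops out. That counts gradings made under the wording and says nothing about how many would be wrong. Disagreement between centers is likewise possible, but nothing in the documents shows that it would happen.

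**Conclusion.** The mismatch is real and follows from the text alone: as written, the item's qualifier contradicts the trial's treatment and its prohibited-medication list, and it omits the cause that a tolerability measure most needs. The consequence is minor. It is confined to the erythema score, one of six tolerability items. It leaves the efficacy endpoints untouched and is partly covered by adverse event reporting. The frequency of discrepant scores cannot be estimated from the documents.

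That redness from the gel goes ungraded rests on one assumption: that a rater follows the parenthesis rather than the anchors. The contradiction between sections needs no such assumption.

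**What to change.** Delete the parenthesis in Section 6.2.2, or replace it with *(truncal redness regardless of cause)*, and apply the same wording at all visits including baseline. If the CRF repeats the phrase, change it there too; the CRF is not among the documents, so this needs checking. Either edit brings the instruction into line with its colour anchors. Wording that refers to the treated area is best avoided: the Visit 1 list places the assessments before dispensing, so there is no treated area at baseline, and 6.2.2 sets no such limit now.

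The cost is one phrase, with no new visit or assessment. The drawback is that an all-cause score in a single-arm study does not separate gel irritation from acne redness. Change from baseline in the erythema score can be summarised from data already collected, which shows whether redness rose or fell but still not why.

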6.2.3 Vital Signs

the investigator will measure vital signs (SBP; DBP; HR; 1-) and weight as per his standard of care.

7 ASSESSMENTS OF SAFETY

7.1 Safety Assessments

Throughout the study, subjects will be monitored for signs and symptoms of adverse events. An adverse event is any pathological or unintended change in the structure, function or chemistry of the body that occurs during the study, irrespective of causality, including any illness, injury, toxicity, sensitivity, or sudden death. The condition must either not be present pre-study or must worsen in either intensity or frequency during the study.

A serious adverse event is any untoward medical occurrence, that, at any dose:

- results in death;
- is life-threatening;
- requires in-patient hospitalization or prolongation of existing hospitalization;
- results in persistent or significant disability/incapacity;
- is a congenital anomaly/birth defect; or
- is an important medical event.

An unexpected adverse event is any treatment-related adverse event, which is not identified in nature, severity, or frequency in current literature on the test product.

7.2 Reporting Requirements

7.2.1 Serious and/or Unexpected Adverse Events

Any serious or treatment-related unexpected adverse event occurring in this study must be reported to the IRB within its stipulated reporting timelines.

7.2.2 Adverse Event Reporting

All adverse events must be recorded by the Investigator into the CRF. The Investigator will be required to describe the adverse event, onset and stop date, severity, the course of action taken, if any, as well as any pertinent data necessary to allow a complete evaluation of the adverse event. For serious adverse events, an additional report (SAE report) must be completed.

7.2.3 Follow-up and Final Reports

Subjects who have had a serious adverse event must be followed clinically until all parameters, including laboratory values (if applicable), have either returned to normal or are otherwise explained.

If death was the outcome of the event on the initial SAE Report, a Follow-up/Final Report, including autopsy report, when performed, must be completed.

8 STATISTICS

8.1 Sample Size Justification

A total of 30 subjects will be entered into the study. This is a pilot study and a formal justification for the sample size is not provided. The data from this study will provide important data for determining any trends regarding the safety and efficacy of study medication.

8.2 Analyses

Statistical analyses will be conducted on an intent-to-treat basis (i.e., all enrolled subjects will be included in the analyses). All statistical tests will be two-sided and interpreted at a 5% significance level. Descriptive statistics (i.e., mean, standard deviation, etc.) will be provided for all continuous variables and frequencies for all categorical variables collected in this study. These will be presented by treatment group. Summary tables will be used to present patient population characteristics at Baseline; data from the study questionnaires will be included. The incidence and severity of adverse and/or unexpected events will be tabulated and a complete listing of all reports of adverse and/or unexpected events will be presented.

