4.3 Withdrawal of Subjects

It is the right and duty of the Investigator to discontinue the study participation of a subject when the subject's health or well-being is threatened by continuation in the study. Such subjects should be withdrawn from the study.

The following are circumstances that would result in the subject's discontinuation from the study:

- the subject experiences a serious adverse event rendering them unable to continue study participation;
- the subject is unable to physically or mentally tolerate the use of the test medication:
- an exclusion criterion becomes apparent at any time during the study; or
- the subject voluntarily withdraws.

In the event of premature discontinuation from the study, the Investigator should determine the primary reason for discontinuation. A subject who is withdrawn from the study prior to initiation of treatment may be replaced.

TREATMENT OF SUBJECTS AND FOLLOW-UP 5

5.1 **Study Procedures**

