5.3 Concomitant Medication/Treatment

Please see Supplement I for a listing of prohibited medications. Necessary therapies that will not interfere with the response to treatment may be provided at the discretion of the Investigator. The use of any concurrent medication, prescription or over-the-counter drug, is to be recorded in the CRF along with the reason the medication was taken.

ACZ1601 (01JUN2016) Page 8 of 14

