6 STUDY ASSESSMENTS

6.1 Primary Endpoint

The primary endpoint of this study is the percent of patients who achieve a two grade improvement and clear or almost clear on IGA scale for truncal acne.

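### Prohibited acne therapy has no consequence in the analysis, so a subject who uses it and reaches IGA 0 or 1 counts as a success for the gel

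*Combined protocol and SAP*

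**What the plan says.** Section 6.1 gives the primary endpoint as the "percent of patients who achieve a two grade improvement and clear or almost clear on IGA scale for truncal acne". It sets no condition on other treatment. Subjects enter at truncal IGA 3 (section 4.1), so a two-grade improvement and a score of 0 or 1 are the same event.

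Section 8.2 adopts intent-to-treat, explained as "all enrolled subjects will be included in the analyses". It defines no other analysis set, no non-responder rule and no sensitivity analysis.

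Supplement I lists topical and oral acne treatments and skin procedures that "are prohibited during the course of the study", with wash-out periods before Visit 1. It does not say what happens in the analysis if one is used later.

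Section 4.3 introduces its list with "The following are circumstances that would result in the subject's discontinuation from the study". Starting a prohibited therapy is not on the list.

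Section 5.3 says "The use of any concurrent medication, prescription or over-the-counter drug, is to be recorded in the CRF", with the reason. Use of a prohibited therapy can therefore be identified from data already collected.

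**The concern.** The trial wants to know how often truncal acne clears on this gel. The endpoint as written counts clearance whatever else the subject used. A subject who adds, say, an oral retinoid or a course of oral antibiotics for acne and then reaches IGA 0 or 1 meets the definition in 6.1, belongs to the analysis set in 8.2, and is credited to the gel. The same subject's lesion counts enter the percent reductions in 6.2 unchanged.

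In a randomised comparison some of this might be balanced between arms. Here every subject receives the gel, so any success owed to another therapy goes straight into the reported rate. The study is also open-label: if no rule is set beforehand, the classification of such subjects will be chosen when their results are already known.

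**Working it through.** **The plan's own figure.** The only design figure is the sample size: "A total of 30 subjects will be entered into the study". There is nothing to reproduce, since "a formal justification for the sample size is not provided". No reference rate, effect size, power or dropout is given.

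**Step 1: follow one subject through the text.** The subject is enrolled at IGA 3, starts a Supplement I acne therapy after Visit 1, stays on study and is scored 1.
- Section 4.3: use of prohibited therapy is not listed. The nearest item is an exclusion criterion that comes to light during the study. The exclusion criterion that cites Supplement I concerns wash-out compliance, and every wash-out in that table is a period before Visit 1.
- Section 8.2: the subject is enrolled, so is analysed.
- Section 6.1: 3 - 1 = 2 grades, and the score is 1, so the subject is a success.

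Withdrawing the subject would not settle the matter, because 8.2 keeps all enrolled subjects and no section says how a withdrawn subject's IGA is classified.

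**Step 2: shift per subject.** Let k be the number of subjects who used prohibited therapy and were scored 0 or 1. Compared with counting them as non-responders, the shift is k/30:
- k = 0: 0 points
- k = 1: 1/30 = 3.3 points
- k = 2: 2/30 = 6.7 points
- k = 3: 3/30 = 10.0 points

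**Step 3: expected shift.** Let q be the share of subjects who use prohibited therapy and c the share of those who reach IGA 0 or 1. The expected shift is q × c. The documents give neither quantity, so the values below are assumptions.
- q = 0: 0 points for any c
- q = 5%: 0.05 × 0.30 = 1.5 points to 0.05 × 0.80 = 4.0 points
- q = 10%: 0.10 × 0.30 = 3.0 points to 0.10 × 0.80 = 8.0 points

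**Step 4: illustration with exact (Clopper-Pearson) 95% intervals.** Assume 9 of 30 are counted as responders, and k of the 9 used prohibited therapy.

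| k reclassified | Responders | Rate | 95% CI |
|---|---|---|---|
| 0 | 9/30 | 30.0% | 14.7 to 49.4 |
| 1 | 8/30 | 26.7% | 12.3 to 45.9 |
| 2 | 7/30 | 23.3% | 9.9 to 42.3 |
| 3 | 6/30 | 20.0% | 7.7 to 38.6 |

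The half-width at 9/30 is (49.4 - 14.7)/2, about 17 points, so shifts of 3.3 to 10 points are smaller than the sampling uncertainty.

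**The case against.** The strongest reply is that the plan contains no faulty rule, only a silence. A reader might infer from 8.2 that subjects are to be scored as observed whatever else they used. The section does not say so. Its intent-to-treat sentence settles who is analysed, not how they are classified, and it is fully compatible with counting these subjects as non-responders. This stands. The problem comes from the unconditional endpoint in 6.1 combined with the lack of any rule elsewhere, and the analysis set need not change.

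Second, the scenario needs a protocol deviation. Supplement I forbids it, 5.3 allows only necessary therapies that do not interfere with the response, 4.2 excludes subjects with a record of poor compliance, and 9.1 binds investigators to the protocol. These controls may keep the number small, possibly zero, but none gives a deviation a status in the analysis.

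Third, a reader might infer that every success in a user is owed to the other therapy. The documents do not support that. A subject who would have cleared on the gel alone adds no inflation relative to the gel's true effect, and a non-responder rule is too strict for that subject. This also stands, and is the reason to report both results.

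Fourth, this is a 30-subject pilot looking for trends, with no reference rate or success threshold, so no stated decision would change. That limits the consequence to interpretation. The wide interval is only a partial defence, since it describes sampling error and not misattribution.

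**Conclusion.** The point holds as an inexpensive improvement to the primary analysis. Read literally, 6.1 and 8.2 credit the gel with an IGA success reached on prohibited therapy, and nothing elsewhere reverses this.

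The firm figure is 3.3 points per affected subject, which rests only on N = 30 and on a non-responder rule as the comparison. Against that rule the shift can only be zero or upward. The range of about 1.5 to 8 points rests on assumed rates of 5-10% use and 30-80% clearance among users; with no use it is zero.

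A much larger effect is tempting to quote: six users who all clear would give 6/30 = 20 points. That would need one subject in five to break the prohibition and every one of them to clear, and nothing in the documents supports either figure.

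**What to change.** Add to 6.1 and 8.2 that a subject who uses a Supplement I acne therapy or procedure after Visit 1 and before the primary IGA assessment stays in the intent-to-treat denominator and counts as a non-responder for the primary endpoint. Bleaching agents, which Supplement I also lists, should not trigger the rule, and the study gel itself must be excepted from the topical dapsone entry. Section 6.1 names no visit for the primary IGA, so the sentence should name it. Report the response rate regardless of such use as a sensitivity analysis.

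For the lesion counts in 6.2, keep all enrolled subjects in the main summary and add a sensitivity analysis that sets users' week-16 percent reduction to zero. Excluding users' counts would be worse: if users are mainly subjects doing poorly on the gel, the remainder responds better and the mean reduction could rise.

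The cost is a few sentences and the sensitivity results. No new data are needed, since the CRF already records concurrent medication with its reason. The downside is that the reported rate may be slightly lower, and the rule is conservative for a user who would have cleared on the gel alone. The change concerns analysis only and leaves clinical management as it is.

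### Frequencies of the tolerability grades can mask new or worsening erythema, because acne-related redness may clear in some subjects while others get redder; 8.2 should add baseline shift tables

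*Combined protocol and SAP*

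**What the plan says.** - **Planned analysis.** Section 8.2 provides descriptive statistics for continuous variables and "frequencies for all categorical variables collected in this study". It names no change from baseline, shift table or worst post-baseline grade for tolerability. It sets a general testing rule ("All statistical tests will be two-sided and interpreted at a 5% significance level") but assigns no test to these scales.
- **The scales.** Section 6.2.2 has the investigator grade the "severity of erythema (disease related and/or related to retinoid use), dryness, peeling, and oiliness" from 0 to 4, and grade pruritus and burning from 0 to 5 by interview. The schedule in 5.1.1 places tolerability at baseline and at Weeks 4, 10 and 16.
- **Expected effects.** Section 1.1 includes erythema among the possible adverse effects of the gel. Oiliness is not in that list.
- **Adverse events.** Section 7.1 measures these against the pre-study state: "The condition must either not be present pre-study or must worsen in either intensity or frequency during the study". Section 7.2.2 requires all of them to be recorded with severity and dates, and 8.2 tabulates and lists them.
- **Design.** One open-label arm: "All study subjects will receive Aczone gel 7.5% at Visit 1". On size: "A total of 30 subjects will be entered into the study", without formal justification (8.1).

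**The concern.** By the protocol's own wording, one erythema grade can carry two signals. Disease redness should decline if the acne responds; redness caused by the gel would increase. A frequency table for each visit adds these across subjects and reports only the net result. Mean grades would do the same.

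Safety is half of the objective in section 2, and the tolerability scales are the study's structured, graded measure of local effects. If the erythema table shows a falling percentage, a reader could take it as good tolerability when some subjects had become worse. The lesion-count endpoints in 6.2 are defined against baseline. The tolerability grades are not, although the paired data will exist.

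**Working it through.** The documents contain no tolerability figure to reproduce, so the check asks what marginal frequencies can and cannot show.

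**Inputs**
- N = 30, from 8.1.
- b = share with erythema of grade 1 or more at baseline. Not given; assumed range 20% to 80%, plus the limiting case of zero.
- c = share of those whose erythema resolves by follow-up. Not given; assumed range 30% to 70%.
- e = share of the initially unaffected who become affected. Not given; assumed range 10% to 40%.

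**Formulas**
- Frequency at follow-up: f = b(1 − c) + (1 − b)e.
- Newly affected, as a share of all subjects: (1 − b)e.
- The frequency does not rise when c ≥ (1 − b)e/b.

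**Results**

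| b | c | e | f | Change in frequency | Newly affected, of all |
|---|---|---|---|---|---|
| 0% | – | 20% | 20% | +20 points | 20% |
| 20% | 50% | 20% | 0.10 + 0.16 = 26% | +6 points | 16% |
| 20% | 70% | 10% | 0.06 + 0.08 = 14% | −6 points | 8% |
| 50% | 30% | 40% | 0.35 + 0.20 = 55% | +5 points | 20% |
| 50% | 50% | 20% | 0.25 + 0.10 = 35% | −15 points | 10% |
| 50% | 50% | 40% | 0.25 + 0.20 = 45% | −5 points | 20% |
| 80% | 50% | 40% | 0.40 + 0.08 = 48% | −32 points | 8% |

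With e = 20%, the resolution that keeps the frequency from rising is 0.8 × 0.2/0.2 = 80% at b = 20%, 0.6 × 0.2/0.4 = 30% at b = 40%, 0.5 × 0.2/0.5 = 20% at b = 50%, and 0.2 × 0.2/0.8 = 5% at b = 80%. A higher baseline prevalence makes masking easier but leaves fewer subjects who can be newly affected. The formula counts only new onset; worsening from grade 1 upwards comes on top.

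**In counts (assumed).** Of 30 subjects, 15 have erythema at baseline, 10 of these resolve, and 6 of the 15 unaffected develop it. Follow-up count: 15 − 10 + 6 = 11. The frequency falls from 15/30 (50%) to 11/30 (37%). A shift table would show 6/30 = 20% newly affected, exact 95% CI 7.7% to 38.6%.

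**What the margins alone allow.** With A affected at baseline and B at follow-up, the number newly affected lies between max(0, B − A) and min(B, N − A). For A = 15 and B = 11 that is 0 to min(11, 15) = 11. For A = 20 and B = 15 it is 0 to min(15, 10) = 10. The planned table cannot say where in these ranges the truth lies.

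**The case against.** **Adverse events already cover worsening.** They are defined against the pre-study state, assessed at every follow-up visit, and both tabulated and listed. This stands in part, and it rules out the stronger inference that the safety objective would rest on the tolerability grades alone. The protection is incomplete because no rule says when a higher grade must be recorded as an adverse event, and investigators at three centers could differ.

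**The documented overlap covers one item of six.** This stands. Only erythema is described as possibly due to the disease and also listed as a gel effect. A reader might infer the same of oiliness, but the documents tie it neither to acne nor to the gel. For the other items, if few subjects are affected at baseline, ordinary frequencies would rise with irritation and show it.

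**Frequencies by visit do show a peak.** This stands. A reader might think that a subject at their worst at Week 4 and settled by Week 16 goes unseen, but that subject is counted at Week 4. What is missing is the link to the subject's own baseline. A table of all grades would also show any severe ones.

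**8.2 does not forbid a shift table.** True, since a shift table is itself a frequency table, and it could be produced at reporting. But it is not planned, and choosing the presentation after seeing open-label data invites the more favourable one.

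**Worst grade against baseline would mislead as the main summary.** This stands. If grading noise alone gave a one-grade rise at a visit with an assumed probability of 10% to 20%, independently across three visits, then 1 − 0.9³ = 27% to 1 − 0.8³ = 49% of subjects would count as worse with no drug effect. It belongs in a supporting role.

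**Conclusion.** The point holds for erythema, as a gap in the planned summaries. Frequencies can stay flat or fall while individual subjects newly develop redness or worsen. Within the assumed ranges, at 50% baseline prevalence the frequency can drop by 5 points while 20% of all subjects are newly affected. At 20% prevalence masking is often incomplete, and at zero it cannot occur. The true baseline prevalence, resolution and onset are unknown, so the documents support a risk of masking, not a finding that irritation will be hidden.

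A reader might also expect a baseline-referenced table to isolate irritation caused by the gel. With no control arm it cannot: it shows who worsened, not why. In a 30-subject pilot with no tolerability test named, this is a low-cost improvement rather than a threat to the primary result.

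**What to change.** In 8.2, add for each of the six tolerability items:

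1. A shift table of baseline grade by grade at each of Weeks 4, 10 and 16, with a category for missing grades.
2. The number and percent of all subjects whose grade exceeds their own baseline by at least 1, and by at least 2, at each visit, with exact 95% confidence intervals.
3. As a supporting summary, worst post-baseline grade against baseline. State that taking the worst of three visits inflates apparent worsening through grading variation, and that without a control arm worsening cannot be attributed to the gel.

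Keep the frequencies by visit. No visits, subjects or assessments are added. The cost is a few more tables and a tolerability profile that may look less favourable.
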